6.1.1. JUSTIFICATION OF SAMPLE SIZE

In Part 1, patients will be recruited sequentially in separate increasing dose groups, with each group randomizing 6 patients to a specific dose of TB006 and 2 randomized to placebo. If all 3 planned dose levels are investigated, the study will recruit approximately 24 patients in total (18 receiving TB006 treatment at the different dose levels, and 6 receiving placebo).

In Part 2, patients will be randomized to TB006 or placebo in a 1:1 ratio so that approximately 58 patients will be randomized to each group. Randomization in Part 2 will be stratified according to baseline patient severity, with mild AD patients (MMSE 21-24) and moderate-severe AD patients (MMSE ≤ 20) in each stratum. Patients enrolled at the same TB006 dose level in Part 1, as well as all placebo patients, will be included in the efficacy analyses in Part 2. Thus, the number of patients in each group for the primary efficacy analysis will be approximately 64.

Assuming that the standard deviation (SD) of change from baseline (CFB) Clinical Dementia Rating Scale (CDRS) - Sum of Boxes at Day 104 is 0.5, a total of 128 patients will provide 80% power to detect a mean CFB difference of 0.25 at Day 104 using a 2-sided, 2 sample t-test at the 5% level of significance.

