6.4. PHARMACOKINETIC ENDPOINTS

The PK analysis will be performed using PK parameters derived by non-compartmental analysis (NCA) using the TB006 plasma concentration time data. The PK parameters will be estimated using actual sampling time relative to the start of infusion.

For Part 1 of the study, the PK analysis will be performed as primary endpoint and includes, but not limited to:

- Area under the concentration time curve from time zero to the 6-hour post end of infusion timepoint (AUC₀₋₆) (Days 1, 8, and 29)
- Area under the concentration time curve over a dosing interval (AUC_τ) (Days 1 and 29)
- Area under the concentration-time curve from zero time to the last measurable time point (AUC_{0-*last*}) (Day 29)
- Maximum observed plasma concentration (C_{max}) (Days 1, 8, and 29)
- Time at which maximum plasma concentration occurs (t_{max}) (Days 1, 8, and 29)
- Concentration at the end of a dosing interval (C_{trough}) (Days 8, 15, 22, 29, and 36)
- Terminal elimination phase half-life (t_½) (Day 29 only)
- Total clearance (CL), calculated as dose/AUC_τ. (Day 29 only)
- Volume of distribution (V_d), calculated as dose/kel × AUC_τ, where kel is the apparent elimination rate-constant, computed by log linear regression of the terminal log linear segment of the plasma concentration versus time curve (Day 29 only).

[figure not shown]
The extent of CSF distribution as estimated by TB006 CSF concentrations on Day 36 will also be determined.

For Part 2 of the study, the PK analysis will be performed as secondary endpoint and will include:

- Maximum observed plasma concentration (C_{max}) (Days 1, 8, and 29)
- Concentration at the end of a dosing interval (C_{trough}) (Days 29 and 36)
- Area under the concentration-time curve from zero time to the last measurable time point (AUC_{0-*last*}) (Day 29)
- Terminal elimination phase half-life (t_½) (Day 29 only)

Note that no CSF will be collected in Part 2 of the study.

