9. OVERALL STATISTICAL CONSIDERATIONS

9.1. GENERAL CONVENTIONS

Summary statistics will be presented for categorical data as number and percentage [n (%)] where the percentage is displayed to one decimal point (e.g., 98.1).

Descriptive statistics will be presented for continuous data with applicable decimal precision as follows in relation to the source data (indicated as N), with a maximum of three decimals to be displayed:

- Number (n).
- Mean, (N+1).
- SD, (N+2).
- Median, (N+1).
- Minimum, (N+0).
- Maximum, (N+0).

Study day is calculated relative to the first dose of study drug infusion and will thus in most cases coincide with the visit naming (e.g., Day 1 will be on study day = 1, Day 15 will be on study day = 15 etc.)

- If the current assessment/collection/result (ACR) date is on or after first dose of study drug infusion:

$$\text{Study Day} = (\text{Current ACR Date} - \text{First dose of Study Drug infusion Date}) + 1$$

- If the current ACR date is before first dose of study drug infusion:

$$\text{Study Day} = (\text{Current ACR Date} - \text{First dose of Study Drug Infusion Date})$$

Study day will not be calculated if either the current ACR or the first dose of study drug infusion date is incomplete or missing.

All the tables in Part 1, will be displayed by treatment groups (i.e., TB006 140 mg qw, TB006 420 mg qw, TB006 1000 mg qw, and Pooled placebo).

The dispositions, efficacy, PK/PD, biomarker, and immunogenicity analysis for Part 2 will be classified by treatment groups (i.e., TB006 and Placebo) and baseline AD severity stratifications [i.e. mild AD (MMSE 21-24) and moderate-severe AD (MMSE ≤ 20)]. For efficacy tables of Part 2, the subjects enrolled at the same TB006 dose level in Part 1, as well as all placebo patients will be included.

For all baseline, safety and efficacy assessments, the subjects will be tabulated using the actually received treatment. For example, if there is a subject who is planned to receive TB006 but accidentally gets treated with one of the other regimens, the subject will be tabulated under the other regimen actually received.

The tables and listing for both protocol parts will be presented separately. The detailed layout will be presented in mock shell.

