10.5. PHARMACOKINETICS

The following PK listings are planned for presentation (PKS) for both protocol parts:

- TB006 plasma concentration levels
- TB006 CSF concentration level (Part 1 only)
- Pharmacokinetic parameters of plasma TB006
- Dose-normalized plasma exposure PK parameters (AUCs and C_{max}) – (Part 1 only).

The following descriptive summary tables are planned to be presented for subjects who received TB006 (PKS), by treatment groups and baseline AD severity stratifications (for Part 2 only):

- Plasma concentration of TB006 at each time points
- CSF concentration of TB006 at each time points (Part 1 only)
- Plasma PK parameters
- Dose-normalized exposure PK parameters (AUCs and C_{max}) (Part 1 only, Days 1, 8, and 29, as applicable)
- Power model slope estimate for dose proportionality assessment (including 95% CI) (Part 1 only)

Figures of the following PK items are planned for presentation (PKS) for both protocol parts:

- Overlaid individual plasma concentration versus time plots (linear and semi-logarithmic scale) by treatment groups

- Overlaid mean plasma concentration versus time plots, presented by treatment groups (linear scale with and without SD)
- Overlaid mean plasma concentration versus time plots, presented by treatment groups (semi-logarithmic scale with and without SD)
- Boxplots of dose-normalized PK parameters (AUCs and C_{max}), grouped by treatment groups grouped within each figure (Part 1 only, Days 1, 8, and 29, as applicable)
- Scatterplots of PK parameters (AUCs and C_{max}), versus dose (as part of power model results), by treatment groups (Part 1 only, Days 1, 8 and 29, as applicable)

Assessment of dose proportionality will be performed by PK Day (Day 1, 8, and 29, as applicable) and will not be based strictly on statistical rule criteria but rather, several factors will be taken into account when assessing dose proportionality, such as:

- Power model results (e.g., the slope estimate and the width of the 95% CIs)
- Graphical evaluation (box plots of dose normalized AUCs and C_{max})
- Descriptive statistics by treatment groups of dose-normalized PK parameters

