Evaluations of the dose proportionality of these parameters will include using the Power Model if there will be at least 3 dose levels available. A statistical linear relationship between the ln-transformed PK parameters and the ln-transformed dose will be fitted by using a mixed model with ln-transformed dose as a covariate and random effect for intercept and subject. Here, (ln-) stands for natural logarithm. Additional predictors may be included in the model. The general form of the Power Model is described as:

$$Ln(Y) = \beta_0 + \beta \ln(Dose) + \varepsilon$$

Where, Y represents the PK parameter (AUCs and C_{max}), and β_0 is constant. This approach is usually referred to as a power model because after exponentiation:

$$Y = \alpha (Dose)^\beta$$

[figure not shown]
Note that $\beta = 1$ would correspond to perfect dose proportionality.

The following example SAS® code can be utilized and modified as needed:

```
Proc Mixed Data = <Dataset>;
  Class <subjectnum>
  Model <lnY> = <lnDose> / ddfm=kr;
  Random <intercept> / subject = <subjectnum> type=UN;
  Estimate 'Logdose - 1 unit' <lnDose> 1/CL alpha=0.05;
  ods output estimates = <estimate>;
Run;
```

Where <Dataset> is the input dataset, <subjectnum> is the subject number, <lnY> is $\ln(Y)$ (Y being the PK parameter in question, <lnDose> is $\ln(Dose)$, <intercept> is the intercept and <estimate> is the output dataset containing the estimate.

The data for these presentations will be obtained from the external PK laboratory data and eCRF.

Descriptive summary tables of biomarker levels from both plasma and CSF (for Part 1 only) collection will be presented, by treatment groups and baseline AD severity stratifications (for Part 2 only), using PDS for both protocol parts, including CFB and CFB% through end of study.

The relationship between dose, Day 29 plasma TB006 PK exposure parameters (AUC_{tau} and C_{max}), Day 36 CSF TB006 concentration and PD biomarkers listed in Section 10.6 will be assessed graphically. Scatter plots of CFB and CFB% will be presented next to another in grid format for PD endpoint values versus TB006 AUC_{tau} and C_{max} . The PD endpoints will be for timepoints Day 36 and end of study. The main measure of interest for consideration will be the CFB of PD biomarkers.

The data for these presentations will be obtained from the external laboratory data and eCRF.

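### The dose-proportionality power model in SAP 10.5 adds a subject intercept that one value per patient cannot support, and it includes AUC0-last, whose end point can move with dose

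*SAP*

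**What the plan says.** **Unit of analysis.** SAP 10.5 states: "Assessment of dose proportionality will be performed by PK Day (Day 1, 8, and 29, as applicable"). The planned output is the "Power model slope estimate for dose proportionality assessment (including 95% CI) (Part 1 only"). Part 1 is a parallel-group escalation with three active levels (SAP 9.1: "TB006 140 mg qw, TB006 420 mg qw, TB006 1000 mg qw, and Pooled placebo"). SAP 6.1.1 has each "group randomizing 6 patients to a specific dose of TB006 and 2 randomized to placebo".

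**Model.** The SAP gives three descriptions that do not agree:
- The text asks for a "mixed model with ln-transformed dose as a covariate and random effect for intercept and subject".
- The example code has "Random <intercept> / subject = <subjectnum> type=UN" on top of the default residual, with Kenward-Roger degrees of freedom.
- The displayed equation is ln(Y) = β0 + β ln(Dose) + ε, with a single error term.

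**Response.** The SAP defines it with "Where, Y represents the PK parameter (AUCs and" Cmax), and excludes no AUC. SAP 6.4 lists among the Part 1 AUCs, for Day 29, the "Area under the concentration-time curve from zero time to the last measurable time point". SAP 9.3 sets values below the quantification limit to missing once a quantifiable value has been seen. After the Day 29 profile, the Part 1 schedule has single PK samples on Days 36, 64 and 104.

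**The concern.** With one observation per patient, a random patient effect and a residual are the same thing twice. The data fix only the sum of the two variances, so the specified model has no unique solution. The programmer must either depart from the text or report a fit that warns of singularity. The SAP is the only pre-specification of this analysis, because SAP Section 8 lists dose proportionality as not mentioned in the protocol.

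The second matter is the response variable. AUC0-last has no fixed interval. If low-dose patients become unquantifiable at an earlier visit than high-dose patients, their area is cut short. The slope then exceeds 1 even when exposure is exactly proportional to dose. The dose-normalised boxplots and summaries would carry the same artefact, so for this parameter they would not act as an independent check.

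**Working it through.** The documents give no precision figure for this analysis, so there is none to reproduce.

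**Inputs.** Doses are 140, 420 and 1,000 mg with 6 active patients each, so n = 18 (SAP 6.1.1, 9.1). ln(dose) is 4.942, 6.040 and 6.908, with mean 5.963. The deviations are −1.022, 0.077 and 0.945. Sxx = 6 × 1.942 = 11.65.

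**1. Variance terms**

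- With one value per patient, the covariance matrix is (σ²subject + σ²residual) × I. Only the sum σ² enters the likelihood.
- In one simulated data set of the planned size, the REML log-likelihood was 17.405 with 0, 10, 25, 50, 75 or 90% of the variance assigned to subject. The slope (0.9367) and SE (0.0507) were the same at every split and equal to ordinary regression.
- The expected information for the two variances has 16/(2σ⁴) in all four cells. It therefore has rank 1 and one zero eigenvalue, and cannot be inverted in the usual way.
- With a generalised inverse, the Satterthwaite-type df is 2(vσ²)² / (v²σ⁴/8) = 16, where v = 1/Sxx. This is the ordinary-regression value, 18 − 2.

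**2. AUC0-last**

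Assume exact proportionality and one-compartment decay from Day 29 with half-life h days. The share of the area captured by day T is F(T) = 1 − 2^(−(T−29)/h). Suppose 140 mg is last quantifiable on Day 64 and the other doses on Day 104. Then ln(AUC) at 140 mg shifts by d = ln[F(64)/F(104)], and the slope shifts by (−1.022/1.942) × d = −0.526 d.

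| h (days) | F(64) | F(104) | area lost at 140 mg | d | slope |
|---|---|---|---|---|---|
| 10 | 0.912 | 0.994 | 8% | −0.087 | 1.05 |
| 12 | 0.868 | 0.987 | 12% | −0.129 | 1.07 |
| 15 | 0.802 | 0.969 | 17% | −0.189 | 1.10 |
| 20 | 0.703 | 0.926 | 24% | −0.276 | 1.14 |

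Protocol 4.3 reports about 10 to 12 days in monkeys and expects longer in humans; 15 and 20 days are assumed values. If all three groups end at the same visit, d is equal across doses and the slope is 1.00.

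**When could this happen?** Neither the assay limit nor the human volume of distribution is given. A rough guide comes from Protocol 4.3: NOAEL AUC of about 135,000 h·µg/mL, with margins of nearly 30-fold at 140 mg and 6-fold at 1,000 mg. Treat these as AUCs over one weekly interval.
- The AUC at 140 mg is 135,000/30 = 4,500, or, scaled down from the top dose, (135,000/6) × 0.14 = 3,150 h·µg/mL.
- With k = ln 2/(24h) per hour, the Day 29 concentration is AUC × k/(1 − 2^(−7/h)). Multiplying by 2^(−75/h) gives Day 104.
- The result at 140 mg is about 0.13–0.19, 0.30–0.43, 0.69–0.98 and 1.6–2.2 µg/mL at h = 10, 12, 15 and 20.

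The tabulated case needs an assay limit between 1 and 3 times those values, since 420/140 = 3. If the limit is higher, so that 420 mg also ends at Day 64, the slopes are 1.04, 1.06, 1.09 and 1.13. In a wider grid of assumed values (limit 0.01–10 µg/mL, volume 3.5–6 L, half-life 6–21 days), limits of 0.1 µg/mL or less gave slopes of 1.00–1.01.

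**Scale.** The slope's 95% CI half-width is t(0.975; 16) × √ln(1 + CV²)/√11.65. With CV assumed at 20, 30, 40 and 60%, this is 0.12, 0.18, 0.24 and 0.34.

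**The case against.** The strongest reply is that nothing reported is shown to change. The listed output is the slope and its CI, and both match ordinary regression. The code is offered as an example that may be altered, and the displayed equation is already the right model. The assessment follows no strict rule, the power model is one of several factors, and no escalation or dose-selection decision is tied to the slope. All of this stands, and it sets the severity. It does not remove the defect: the random effect is in the SAP text as well as in the code, so altering the example alone leaves the contradiction.

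It might also be said that the example code has no BY statement, and that a subject effect would be estimable if PK days were pooled. The text, however, specifies analysis by PK day, the code has no day term, and AUC0-last exists only for Day 29.

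Two stronger readings are tempting:
- *The confidence interval will be wrong or too narrow.* A reader might infer this from the singular variance model. The documents do not support it. The SE depends only on the identified sum of variances, and software that prints another value from a singular matrix has a reporting failure of its own. SAS was not run, so its exact handling is not shown.
- *The AUC0-last slope is biased upward.* This holds only if the end visits differ by dose, which turns on an assay limit the documents do not give. The 1.14 figure also needs the highest limit in the table, about 1.6–2.2 µg/mL or more. Every tabulated shift lies within the 0.18 half-width at an assumed 30% CV. AUCtau, AUC0-6 and Cmax do not share the moving end point, so a discrepancy could be noticed.

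**Conclusion.** The point holds as a minor specification error in two parts.

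- **Random intercept:** this part is certain, because it follows from having one value per patient per fit. The consequence is an ill-posed model, likely singularity warnings, arbitrary variance components and a mismatch with the displayed equation.
- **AUC0-last:** this part is conditional. Under true proportionality, the slope is about 1.05 to 1.14 at half-lives of 10 to 20 days if 140 mg ends at Day 64 and the others at Day 104. It is 1.00 if all groups end together. The figures assume one-compartment decay and an assay limit that separates the doses at Day 104.

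A reader might infer that the primary PK objective of Part 1 is compromised. The documents do not support that, since dose proportionality is not among the stated objectives and is a supportive addition in the SAP.

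**What to change.** 1. In SAP 10.5, delete the RANDOM statement and the wording that asks for random effects. Fit ln(Y) on ln(dose) by ordinary regression for each PK day, as the displayed equation already implies (16 residual df with 18 patients).
2. Restrict the power model and the dose-normalised comparisons to AUCtau, AUC0-6 and Cmax, all already planned in SAP 6.4. Alternatively, cut the Day 29 AUC at a common day that is quantifiable in all dose groups. Keep AUC0-last as a descriptive parameter.

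The cost is two wording changes and a simpler program, with no new data.

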10.7. TREATMENT COMPLIANCE AND EXPOSURE

A listing of subject exposure to all the doses of TB006 will be presented including the date/time of dose and dose level exposed to (SAS) for both protocol parts separately. Also, the treatment compliance information will be listed.

A table containing summary statistics of dose level exposure, by treatment groups will also be presented using SAS.

Treatment compliance is defined as the number of IV doses (including partial doses, active and placebo) actually received divided by the number of doses expected ($\times 100$) over the time period defined by the first infusion date and the last dose date.

Descriptive statistics for treatment compliance and the number and percentage of subjects with at least 80% compliant will be presented using SAS.

The data for these presentations will be obtained from the Study drug infusion eCRF.

11. EFFICACY PARAMETERS

All the efficacy analysis planned for Part 1 will be performed using PDS and efficacy analysis planned for Part 2 will be performed using EAS2. The EAS2 include all PDS subjects of Part 2, placebo subjects of Part 1 and subjects with same dose level in Part 1 pooled together.

11.1. PRIMARY ANALYSIS

There is no primary efficacy analysis planned for Part 1.

For Part 2, the CFB through Day 104 on the CDRS – Sum of Boxes total score is primary efficacy endpoint, and it will be analyzed using MMRM with treatment group, randomization strata (MMSE \leq 20 and 21-24), visit, and treatment group (treated vs. placebo) by visit interaction as fixed effects and a baseline CDRS - Sum of Boxes score as a covariate. The LS mean difference, the 95% CI of the difference, and the p-value will be presented as well as the descriptive statistics.

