5.1 Inclusion Criteria

Patients are eligible to be included in the study only if all of the following criteria apply:

- 1. Male and/or female > 50 years of age at the time of signing the informed consent.
- 2. Body weight of \geq 50 kg and BMI between 18 and 35 kg/m², inclusive.
- 3. MMSE score of 24 or less.
- 4. Must be ambulatory.
- 5. Clinical diagnosis of AD consistent with the following:
 - a. Probable AD, according to NINCDS-ADRDA (Section 10.5 [Appendix 5])
 - b. Meets the DSM 5 Criteria for Major Neurocognitive Disorder (previously dementia) (Section 10.4 [Appendix 4])
- 6. Contraceptive use by men should be consistent with local regulations regarding the methods of contraception for those participating in clinical studies.
 - a. Male patients:

Male patients are eligible to participate if they agree to the following from the first day of dosing through 6 months following the last dose of study drug:

- Refrain from donating sperm PLUS, either:
- Be abstinent from heterosexual intercourse as their preferred and usual lifestyle (abstinent on a long term and persistent basis) and agree to remain abstinent unless partner is not a WOCBP

OR

- Must agree to use contraception/barrier as detailed below:
 - Agree to use a male condom and female partner use of an additional highly effective contraceptive method with a failure rate of < 1% per year when having sexual intercourse with a WOCBP who is not currently pregnant.
- b. Females must be of non-childbearing potential defined as:
 - At least 12 months post-menopausal
 - Surgically sterile, resulting from but not limited to tubal ligation, hysterectomy, and oophorectomy.
 - Documented infertility from other causes, such as endometriosis or uterine fibroids.

Protocol TB006AD2102

Protocol Date and Version: 15 Oct 2021; v 3.0

• The investigator is responsible for review of medical history, menstrual history, and recent sexual activity to decrease the risk for inclusion of a woman with an early undetected pregnancy.

- 7. Patients or caregiver has the ability to understand the purpose and risks of the study and provide signed and dated informed consent as described in Section 10.1.3 (Appendix 1) which includes compliance with the requirements and restrictions listed in the ICF and in this protocol. Patients whose caregiver signs the informed consent must provide their assent.

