- 8. May or may not be receiving 1 or more of the currently marketed cognition enhancing AD medications, including, but not limited to donepezil, memantine, rivastigmine, and galantamine. If receiving, it must be the same medication and dose the past 2 months prior to screening.
- 9. Either currently or previously (in pre AD condition) literate and capable of reading, writing, and communicating effectively with others.

Protocol TB006AD2102

Protocol Date and Version: 15 Oct 2021; v 3.0

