9.2 Sample Size Determination

In Part 1, patients will be recruited sequentially in separate increasing dose groups, with each group randomizing 6 patients to a specific dose of TB006 and 2 randomized to placebo. If all 3 planned dose levels are investigated, the study will recruit approximately 24 patients in total (18 receiving TB006 treatment at the different dose levels, and 6 receiving placebo).

In Part 2, patients will be randomized to TB006 or placebo in a 1:1 ratio so that approximately 58 patients will be randomized to each group. Randomization in Part 2 will be stratified according to baseline patient severity, with mild AD patients (MMSE 21-24) and moderate-severe AD patients (MMSE \leq 20) in each strata. Patients enrolled at the same TB006 dose level in Part 1, as well as all placebo patients, will be included in the efficacy analyses in Part 2. Thus, the number of patients in each group for the primary efficacy analysis will be approximately 64.

Assuming that the standard deviation of change from baseline Clinical Dementia Rating Scale – Sum of Boxes at Day 104 is 0.5, a total of 128 patients will provide 80% power to detect a mean change from baseline difference of 0.25 at Day 104 using a 2-sided, 2 sample t-test at the 5% level of significance.

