9.5. MMRM METHOD

The primary and secondary efficacy endpoints associated with efficacy assessments listed in Section 9.4.2 will be analyzed using a MMRM model. The model will include treatment group, visit, stratification factor (MMSE \leq 20 and 21-24), and treatment by visit as fixed effects and associated baseline assessment as covariate. The model will use visit as repeated component in the model.

An unstructured (UN) covariance structure will be applied for the MMRM. In the event the UN covariance matrix results in non-convergence of the model, then the Heterogeneous Toeplitz (TOEPH) and auto regressive [i.e. AR(1)] covariance structures will be used, respectively, with separate subject random effect. The Kenward-Roger (KR) approximation will be used to estimate denominator degrees of freedom.

The least square (LS) mean for CFB and associated 95% confidence interval (CI), and standard error will be presented for each treatment group.

The MMRM model will utilize all available data values for respective efficacy assessments.

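### The primary CDR-SB model uses MMSE only as a two-class stratum and leaves the collected Day -1 score unused: a small efficiency loss

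*SAP*

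**What the plan says.** SAP 11.1 lists the fixed effects of the primary model as treatment group, randomisation stratum, visit and treatment by visit. The baseline value of the outcome is the only continuous term: "as fixed effects and a baseline CDRS - Sum of Boxes score as a covariate". SAP 9.5 gives the same structure for the efficacy scales in general ("as fixed effects and associated baseline assessment as covariate"), and Protocol 9.4.5 agrees with both. The NPI model in SAP 11.2.5 has the same form with baseline NPI. The MMSE-change model in SAP 11.2.4 already uses baseline MMSE as its covariate.

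The entry criterion in Protocol 5.1 is an "MMSE score of 24 or less", with no floor. Protocol 8.6.3.2 gives the scale range as 0 to 30. Protocol Table 2 schedules MMSE at screening and Day -1, and CDR-SB at Day -1 and Days 15, 36, 64 and 104. SAP 11.3 plans no sensitivity analysis, so no other analysis uses a different covariate set.

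**The concern.** The two strata differ greatly in width. The upper one covers 4 scores (21 to 24) and the lower one covers 21 (0 to 20), from near-mild to very severe disease. The stratum term treats everyone in the lower class as equally severe on MMSE. If the MMSE score predicts change in CDR-SB over 104 days beyond what baseline CDR-SB predicts, that variation stays in the residual and widens the confidence interval for the primary difference.

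Two features of the design add some weight. First, about 12 analysed patients (6 at the same dose and 6 on placebo) come from Part 1, and Protocol 6.4.1 describes stratification by MMSE for Part 2 only. Second, Protocol 8.6.3.2 does not require the screening and baseline MMSE to be reconciled. If a site takes the class from screening, it may not match the Day -1 score.

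What is at stake is precision in a trial sized at almost exactly 80% power. The validity of the test is not in question.

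**Working it through.** **Inputs from Protocol 9.2.** Difference: "mean change from baseline difference of 0.25 at Day 104". SD of change: "Sum of Boxes at Day 104 is 0.5". Test: "2-sided, 2 sample t-test at the 5% level of significance". Stated result: "a total of 128 patients will provide 80% power", that is, 64 per arm.

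**Input not in the documents.** The partial R2 of continuous MMSE for Day 104 change, given the stratum and baseline CDR-SB. It is assumed below, with zero included.

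**Step 1: reproduce the plan's figure.** The noncentrality is 0.25 / (0.5 × √(2/64)) = 2.828. On 126 degrees of freedom the two-sided 5% t-test has 80.1% power. At 63 per arm it has 79.5%, so 64 per arm is the exact t-test answer.

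**Step 2: find a plausible range for the increment.** An illustrative simulation set the correlation between MMSE and baseline CDR-SB at -0.6 or -0.75, the mild share at 30% or 50%, and the correlation of MMSE with decline at 0.1 to 0.4. All of these values are assumptions. With stratum and CDR-SB already in the model, continuous MMSE added a partial R2 of about 0.003 to 0.06.

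**Step 3: convert to power.** Adjusted SD = 0.5 × √(1 − R2). Noncentrality = 0.25 / (adjusted SD × √(2/64)). One degree of freedom is charged in the rows with R2 above zero. Equivalent N = 128 / (1 − R2).

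| Assumed partial R2 | Adjusted SD | Noncentrality | Power, 64 per arm | Equivalent total N |
|---|---|---|---|---|
| 0 (plan) | 0.500 | 2.828 | 80.1% | 128 |
| 0.01 | 0.497 | 2.843 | 80.5% | 129 |
| 0.03 | 0.492 | 2.872 | 81.3% | 132 |
| 0.06 | 0.485 | 2.917 | 82.5% | 136 |

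This treats 0.5 as the residual SD of the existing model. The plan's calculation is an unadjusted t-test and takes no credit for baseline CDR-SB, so true starting power may differ.

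**Step 4: cost if MMSE is not prognostic.** Losing 1 degree of freedom moves power from 80.15% to 80.14%. Losing 4 (one MMSE slope per post-baseline visit) moves it to 80.13%. Chance imbalance in a useless covariate also raises the expected standard error by about √(125/124) = 1.004. That takes the noncentrality from 2.828 to about 2.817, or roughly 0.3 point of power. On this reckoning the term pays for itself once partial R2 exceeds about 1 − 124/125 = 0.008.

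**Step 5: why the visit interaction matters.** Suppose the MMSE effect grows linearly with time, and residual variance and between-visit correlation are the same at all visits. A single common slope then settles near the average over the four visits: (15 + 36 + 64 + 104)/4 = 54.75, and 54.75/104 = 0.526 of the Day 104 slope. The share of the Day 104 R2 recovered is 1 − (1 − 0.526)² = 0.775. A nominal 0.06 becomes 0.06 × 0.775 = 0.047, with power about 82.0%. If residual variance also rises with time, early visits carry more weight and less is recovered. The 82.5% is therefore an upper figure for a main effect alone. A visit-specific slope avoids the loss.

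**The case against.** The strongest reply is that the model already contains the two standard adjustments: the randomisation factor and the baseline value of the outcome. Baseline CDR-SB sums six box ratings of 0 to 3 (Protocol 8.6.3.1) and enters continuously, so it separates patients within the lower MMSE class. The stratum term also applies to the pooled Part 1 patients. SAP 9.5, SAP 11.1 and Protocol 9.4.5 agree with one another. All of this stands, and it is why only the increment over CDR-SB and stratum counts.

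Three stronger readings are tempting, but the documents do not support them.

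- **Severity imbalance within the lower class goes uncorrected.** It is corrected as far as baseline CDR-SB reflects severity. Randomisation, not the covariate list, protects the Part 2 comparison from bias.
- **Leaving out background AD medication also loses precision.** Protocol 5.1 does admit a mixed population ("May or may not be receiving 1 or more of the currently marketed cognition enhancing AD medications"). But Protocol 2.2.1 says these symptomatic drugs do not alter progression, though they may help cognition briefly. Protocol 5.1 requires the same drug and dose for 2 months before screening, and Protocol 6.6 steers away from patients whose treatment is expected to change. No expected split between users and non-users is given, and the documents describe medication records rather than a yes/no flag.
- **A gain of about 4 points.** A partial R2 of 0.10 would give 84.1% power, but nothing in the documents supports that value. In the simulation, MMSE alone reached only about 0.06, and that at its most favourable setting.

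**Conclusion.** The point holds as a minor, optional improvement. The primary model reduces MMSE to two classes although the Day -1 score is in hand, and pre-specifying the score could narrow the primary confidence interval slightly. Power at 64 per arm moves from 80.1% to at most about 82.5% for an assumed partial R2 of 0 to about 0.06, the equivalent of up to about 8 patients (136 − 128). If the score adds nothing, the expected loss is about 0.3 point. The range rests on assumed correlations, on reading the plan's SD of 0.5 as the residual SD, and on an MMSE effect that is free to vary by visit. The documents can neither confirm nor exclude a gain of zero. There is no bias, no inflation of type I error and no contradiction between protocol and SAP.

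**What to change.** Before unblinding, add baseline MMSE as a continuous covariate to the CDR-SB model (SAP 9.5 and 11.1) and the NPI model (SAP 11.2.5), preferably with an MMSE-by-visit interaction. Keep the randomisation stratum and the baseline value of the outcome. Use the Day -1 score, which under SAP 9.2 is normally the last value before the first dose. The MMSE-change model needs no MMSE addition. Because Protocol 9.4.5 specifies the present model, list the change and its reason in SAP Section 8.

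Background AD medication may be added as a further covariate if the sponsor wishes. That would need a defined drug list and a baseline rule, and no gain should be claimed for it.

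The cost is a short SAP edit, no new data collection, and 1 degree of freedom for CDR-SB, or 4 with the interaction over four post-baseline visits.
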